9.4.3 Secondary endpoint(s)

For other time-to-event endpoints (time to onset of sustained 20% increase in the 9-HPT, of sustained 20% increase in the T25-FW, of 3-month CDP, and of CDI), similar analysis as for the primary analysis of the primary efficacy endpoint will be performed in the ITT population but without imputation.

Continuous endpoints (percent change in brain volume loss, change in cognitive function, change in physical function, and change in MSQoL-54 at EOS) will be analyzed using a mixed-effect model with repeated measures (MMRM) approach. The model will include change/percent change values for the respective endpoint at each scheduled visit as response variables, and treatment, age at screening (>40, \leq 40 years), geographic region (US, non-US), visit, treatment by-visit interaction, baseline value for the endpoint being assessed and baseline value-by-visit interaction as covariates. Difference in LS means, the corresponding 95% CI, and p-value will be provided for the comparison of SAR442168 versus placebo. For percent change in brain volume loss, log transformation will be applied in the MMRM model. In order to assess the impact of deviation from the normality assumption, a sensitivity analysis using rank ANCOVA with the same covariates as for the MMRM analysis except visit and related interaction terms, will be performed for these continuous endpoints to provide the p-value for the comparison between the treatment groups.

Categorical efficacy endpoints with count data (new and/or enlarging T2 hyperintense over the study period after baseline) will be analyzed using a negative binomial regression model. The model will include the total lesion count across all post-randomization MRI scans during the study period as the response variable, with treatment group, age at screening (>40, \leq 40 years), geographic region (US, non-US), baseline EDSS score, and baseline T2 lesions as covariates. Log-transformed observation duration from screening MRI to last available MRI will be the offset variable. In order to assess the impact of open-label therapy, sensitivity analysis excluding the data after initiation of open-label therapy will be performed for the key secondary endpoints that will be pre-specified in the SAP. Further details including details of missing data handling and subgroup analyses for secondary endpoints will also be detailed in the SAP.

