#### 3.3.1.2.3 Continuous endpoints

Percent change in brain volume at the EOS compared to Month 6 will be analyzed using a mixedeffect model with repeated measures (MMRM) approach in the ITT population for estimating the treatment effect with appropriate transformation if necessary (eg, log-transform). Estimates derived from the MMRM approach will be weighted by overall proportion of participants in

each stratum or categorical factor. The model will include percent change from Month 6 values at scheduled visits up to and including the EOS visit as the response variable, and treatment group, age at screening (>40,  $\leq$ 40 years), geographic region (US, non-US), visit, treatment-by-visit interaction, Month 6 brain volume, and Month 6 brain volume-by-visit interaction as covariates; have an unstructured variance-covariance matrix; and be fitted using restricted maximum likelihood estimation. If this model fails to converge, the following variance-covariance structures will be tested in this order:

- Heterogeneous Toeplitz (Toeplitz with non-equal variances)
- Heterogeneous AR(1) (first-order autoregressive with non-equal variances)
- Heterogeneous CS (compound symmetry with non-equal variances)
- Toeplitz (equal variances and a separate correlation for each level of separation between the time points)
- AR(1) (first-order autoregressive, equal variances and exponentially decreasing correlations)
- CS (compound symmetry, equal variances and equal pairwise correlations across fixed time points).

The first (co)variance structure yielding convergence will be used as the primary analysis. Comparisons between treatment arms will be made using least squares means (LSM) contrasts at the EOS with denominator degrees of freedom estimated using the Kenward-Roger approximation (8). When a variance-covariance structure other than unstructured is used, the denominator degrees of freedom will be estimated using the between within method (DDFM=BW in SAS PROC MIXED) (9).

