Change from baseline in SDMT number of correct substitutions, CVLT-II total correct and MSQoL-54 physical and mental health composite scores at the EOS will be analyzed using an analogous MMRM approach in the ITT population with the change from baseline values for the respective endpoint at scheduled visits up to and including the EOS visit as response variables, and treatment group, age at screening (>40,  $\leq$ 40 years), geographic region (US, non-US), visit, treatment-by-visit interaction, baseline value for the endpoint being assessed and baseline value-by-visit interaction as covariates.

For each endpoint, difference in LSM, the corresponding 95% CI, and p-value will be estimated from the MMRM model for the comparison of tolebrutinib to placebo using weights for each stratum equal to the overall proportion of participants in each stratum (ie, "Population weight"). Plots of LSM [±standard error (SE)] over time will be provided. Participants who discontinue study intervention before the study end will be asked and encouraged to return for all remaining study visits and the additional off-treatment values measured up through the EOS will be included in the primary analysis. For participants who withdraw from the study before the EOS, values will be missing after study discontinuation and no imputation will be performed.

SDMT, CVLT-II and MSQoL-54 data are assumed a priori to be normally distributed. Given the large sample size, the impact of violation of normality should not be great. In order to assess the impact of deviation from the normality assumption, a sensitivity analysis using rank analysis of

covariance (ANCOVA), with the same covariates as for the MMRM analysis except VISIT and related interaction terms, will be performed to test the significance of the treatment effect.

Given that participants who reach the primary endpoint of 6M-CDP are eligible to switch to OL tolebrutinib, including data after the switch could impact the analysis of secondary endpoints: number of new/enlarging T2 lesions per year, time to onset of sustained 20% increase in the 9-HPT (T25-FW) for at least 3 months, and percent change in brain volume at EOS compared to Month 6. Sensitivity analyses excluding data after initiation of OL therapy will be performed for these endpoints.

No other sensitivity, supplementary, or subgroup analyses will be performed for the secondary endpoints.

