#### **Continuous endpoints**

Continuous endpoints include:

- Change from baseline in MSFC-3 Z-score at Months 12, 18, 24, and EOS
- Change from baseline in total volume of T2-hyperintense lesions at Months 18, 24, and EOS
- Change from baseline in EQ-5D-5L descriptive system index score and VAS score by visit

An MMRM method will be used for these endpoints, including covariates of treatment group, age at screening (>40,  $\leq$ 40 years), region (US, non-US), visit, treatment-by-visit interaction, the baseline score, and baseline-by-visit interaction. Least squares means  $\pm$  SE for each treatment group, as well as LSM difference with the 95% CI will be estimated.

Since volume data are often non-normally distributed, analysis of T2 lesion volume will be performed on log-transformed volume data. MSFC-3 and EQ-5D-5L data are assumed a priori to be normally distributed. Given the large sample size, the impact of violation of normality should not be great. In order to assess the impact of deviation from the normality assumption, a sensitivity analysis using rank ANCOVA, with the same covariates as for the MMRM analysis except VISIT and related interaction terms, will be performed to test the significance of the treatment effect.

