#### 3.5 MULTIPLICITY ISSUES

To strongly control the Type 1 error rate for the study, a hierarchical testing procedure will be applied at a 2-sided 5% significance level, ie, each hypothesis will be formally tested only if the preceding one is significant at the 5% level. If statistical significance is achieved for the primary endpoint, a selective set of secondary endpoints will be tested following the hierarchical testing procedure shown below:

- Time to onset of 3-month CDP as assessed by the EDSS score
- Number of new and/or enlarging T2 hyperintense lesions per year
- Time to onset of sustained 20% increase in the 9-HPT for at least 3 months
- Time to onset of sustained 20% increase in the T25-FW for at least 3 months
- Time to onset of CDI confirmed over at least 6 months
- Percent change in brain volume as detected by MRI scans at the EOS compared to Month 6

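### Does the inconsistent wording on log-transforming brain-volume change need correcting?

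*Protocol*

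**What the plan says.** Protocol Section 9.4.3 puts change or percent change into an MMRM for every continuous secondary endpoint, and brain volume is the first one listed. It then adds: "For percent change in brain volume loss, log transformation will be applied in the MMRM model". It also plans a rank-ANCOVA sensitivity analysis, which "will be performed for these continuous endpoints to provide the p-value for the comparison between the treatment groups".

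SAP Section 3.3.1.2.3 specifies the brain-volume model in more detail. "The model will include percent change from Month 6 values at scheduled visits up to and including the EOS visit as the response variable", and the treatment effect is estimated "with appropriate transformation if necessary (eg, log-transform", with log given only as an example. No criterion for necessity is stated. The rank-ANCOVA sentence comes later, in a paragraph that opens "SDMT, CVLT-II and MSQoL-54 data are assumed a priori to be normally distributed". The next paragraph gives brain volume a sensitivity analysis that excludes data after the start of open-label treatment. The section closes with "No other sensitivity, supplementary, or subgroup analyses will be performed for the secondary endpoints".

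SAP Section 3.5 lists "Percent change in brain volume as detected by MRI scans at the EOS compared to Month 6" as the sixth and last secondary endpoint in the hierarchy, tested at the two-sided 5% level.

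**The concern.** The endpoint is formally tested, so its scale should be settled before unblinding. Here one document makes the log mandatory and the other makes it optional. Taken literally, the mandatory version cannot be run, because the stated response is a percent change that will mostly be negative. The SAP does name the logged quantity elsewhere: for an exploratory endpoint in Section 3.4.2, "analysis of T2 lesion volume will be performed on log-transformed volume data". An open transformation clause on a confirmatory endpoint suggests that the scale could be chosen after seeing the data, with a cost in type I error.

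The second worry is the rank-ANCOVA check. On a narrow reading of the SAP it covers only SDMT, CVLT-II and MSQoL-54. Brain volume, the one MMRM secondary endpoint that the SAP does not declare normal, would then lose the distribution-free check that the protocol planned.

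**Working it through.** The plan gives no mean, SD, effect or power for brain volume, so there is no figure to reproduce. All distributional inputs below are assumptions.

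**1. The log of percent change itself.** It is undefined at zero and below. With normal percent change of mean m and SD s, the share of undefined values is Φ(-m/s):

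| Assumed m, s (%) | Share ≤ 0 |
|---|---|
| -0.5, 0.7 | 76% |
| -1.0, 1.0 | 84% |
| -1.5, 1.2 | 89% |
| -2.0, 1.5 | 91% |

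Nobody could run this reading by accident, because most of the data would vanish.

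**2. The log of the volume ratio.** With percent change p, 100 × ln(volume at visit / Month 6 volume) = 100 × ln(1 + p/100) ≈ p - p²/200.

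| p (%) | 100 × ln(1 + p/100) |
|---|---|
| -0.5 | -0.501 |
| -1 | -1.005 |
| -2 | -2.020 |
| -3 | -3.046 |
| -5 | -5.129 |

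The departure from p is second order. Both scales need a Month 6 scan and a later one, and the log ratio exists whenever p exists (p > -100). The choice therefore does not alter who is analysed. This fits the SAP's own convention for T2 lesions, where the volume is what gets logged.

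**3. Type I error.** 40,000 null trials per setting; means -0.8% and -1.5% crossed with SDs 0.8% and 1.5%; arms of 733:367 (the reduced total of 1100 in Protocol Section 9.2, split 2:1) and 500:250 (assuming about one third have no end-of-study scan). A two-sample t-test at end of study stands in for the MMRM. Monte Carlo SE is about 0.1 percentage points.

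| Rule | Rejection at 5% |
|---|---|
| Untransformed | 4.95% to 5.10% |
| Log volume ratio | 4.98% to 5.10% |
| Better p-value of the two | 5.01% to 5.14% |

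The two scales gave different decisions in 0.06% to 0.14% of trials; the minimum correlation was 0.99992.

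**4. Power.** Placebo mean -1%, treatment difference 0.2 SD, 733 versus 367, 1000 runs per SD:

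| SD (%) | Untransformed | Log ratio | Decisions differ |
|---|---|---|---|
| 0.8 | 88.6% | 88.5% | 0.1% |
| 1.2 | 88.9% | 89.0% | 0.1% |
| 2.0 | 89.9% | 90.1% | 0.4% |

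**5. Rank ANCOVA.** The map from p to the log ratio is strictly increasing, so the ranks of the response are the same on either scale and the check gives one answer for both. In the runs of step 4, an unadjusted rank test had power of 85.6%, 87.8% and 88.6%, close to the untransformed test. Those data were normal, so this shows only that the check costs little; it does not test robustness.

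**The case for a change.** The strongest argument is that a third reading exists and would matter: log the absolute loss and drop anyone without a loss. In the runs with a true effect, that reading had 32% to 53% power against about 89% untransformed, and it changed the decision in 37% to 60% of runs. Under the null, taking the better of it and the untransformed test rejected in 7.7% to 9.3% of trials. One sentence would close it off. The SAP also gives its covariance fallback an ordered list and an objective trigger, so the loose transformation clause stands out, and the version history does not record a departure from the protocol.

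Little of this survives. Neither document proposes logging the loss or discarding participants, and discarding them for their outcome would contradict the SAP's statement that this model is fitted in the ITT population. The inflation comes from selecting between p-values: used alone, the log of the loss rejects in 4.8% to 5.3% of null trials. Protocol Section 9.4 also describes itself as a summary and leaves technical detail to the SAP, which is the later document and does fix the response, covariates and covariance sequence.

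On rank ANCOVA, the ambiguity stands. The SAP sentence names no endpoint, and it sits in the section covering all continuous secondary endpoints. The closing exclusion rules out only analyses not already listed, so it does not decide the question. The protocol's wording does include brain volume, and an analyst can follow it. In either case this is a supporting check and not the confirmatory test.

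**Conclusion.** No change is needed. The wording differs between the documents, and the logged quantity is unstated, but this is a gap that any competent analyst fills in one of two ways. Those two ways give the same answer in all but about 0.1% of null trials, with type I error at 5.0% to 5.1% even if the better result were picked. The primary result is unaffected, and because the endpoint is last in the hierarchy no later test inherits anything from it. The doubt about rank ANCOVA concerns the scope of a sensitivity analysis only.

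The simulated figures rest on assumed normal percent changes of roughly -1% with SDs up to 2%, and on t-tests in place of the MMRM. The near-identity of the two scales does not depend on normality; it requires only that changes be small relative to total brain volume. Noting the chosen scale in the programming specification before unblinding would be tidy, but it would not alter what the trial can conclude.

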9.4.4 Tertiary/exploratory endpoint(s)

Methods for analysis of tertiary/exploratory endpoints will be included in the SAP.

9.4.5 Other safety analyses

All safety analyses will be performed on the safety population.

Safety summaries will be descriptive, ie, no statistical significance tests will be performed on safety data. The summary of safety results will be presented by treatment group.

Safety analyses will be based on the reported AEs and other safety information, such as clinical laboratory data, vital signs, and ECG.

The observation period will be divided into 4 epochs:

- The screening epoch is defined as the time from the signed informed consent date up to the first administration of the study intervention.
- The treatment epoch is defined as the time from the first administration of the study intervention to:
 - The earlier of last administration of the study intervention plus 10 days or first IMP in the LTS study for participants not receiving SAR442168 open-label treatment.
 - The first administration of SAR442168 open-label treatment for participants switching to open-label therapy.
- The open-label epoch, applicable only for participants switching to SAR442168 openlabel treatment, is defined as the time from first administration of SAR442168 open-label treatment to the earlier of last administration of open-label treatment plus 10 days or first IMP in the LTS study.
- If applicable, the post-treatment epoch is defined as the time from the end of treatment epoch (or end of open-label epoch, if applicable) to the participant's final study contact date.

The safety analysis of AEs will focus on TEAEs, defined as AEs that developed, worsened, or became serious during the treatment period. All AEs reported in this study will be coded using the Medical Dictionary for Regulatory Activities (MedDRA) version in effect at the time of database lock.

Endpoint	Statistical analysis methods
Adverse Events including AEs, TEAEs, SAEs, AEs leading to treatment discontinuation, AEs leading to death and AESIs	The number and percentage of participants with at least one TEAE, treatment-emergent SAE, TEAE leading to treatment discontinuation, TEAE leading to death, and treatment-emergent AESI will be tabulated by treatment group. Multiple occurrences of the same event in the same participant will be counted only once in the tables. The denominator for computation of percentages will be the safety population within each treatment group. Serious AEs and AEs leading to study discontinuation or death that occur outside the treatment-emergent period will be summarized separately.
Vital signs, laboratory data, and ECG parameters	Descriptive statistics of values and change from baseline values for each parameter will be summarized by treatment group at each time point. The number and percentage of participants with at least one incidence of potentially clinically significant abnormality at any time during the treatment-emergent period will be summarized by treatment group.

Table 4 - Safety analyses

AE: adverse event; AESI: adverse event of special interest; ECG: electrocardiography; SAE: serious adverse event; TEAE: treatmentemergent adverse event

9.4.6 Other analyses

Pharmacokinetic, pharmacodynamic (PD), and biomarker exploratory analyses that will be included in the study report will be described in the SAP. Biomarker research will not be part of statistical analysis in this study and will not be reported in the clinical study report (CSR).

For a regional or national emergency declared by a governmental agency, contingency measures are included in Section 10.10, Appendix 10: Contingency measures for a regional or national emergency that is declared by a governmental agency.

9.5 INTERIM ANALYSES

An optional, non-binding interim futility analysis may be performed when approximately 50% of the primary endpoint events are observed. The futility interim analysis will be conducted by an independent statistics group and reviewed by the DMC. Neither the Sponsor's team nor the Investigator's staff will have access to the treatment information at the individual participant level or group level before the study is formally unblinded after study completion or after the DMC recommendation/Sponsor agreement for stopping the trial.

9.6 DATA MONITORING COMMITTEE (DMC)

For details on the DMC, refer to Appendix 1 (Section 10.1.5).

10 SUPPORTING DOCUMENTATION AND OPERATIONAL CONSIDERATIONS

10.1 APPENDIX 1: REGULATORY, ETHICAL, AND STUDY OVERSIGHT CONSIDERATIONS

10.1.1 Regulatory and ethical considerations

- This study will be conducted in accordance with the protocol and with the following:
 - Consensus ethical principles derived from international guidelines including the Declaration of Helsinki and the applicable amendments and Council for International Organizations of Medical Sciences (CIOMS) International Ethical Guidelines,
 - Applicable ICH GCP Guidelines,
 - Applicable laws and regulations (eg, data protection law as General Data Protection Regulation GDPR).
- The protocol, protocol amendments, ICF, IB, and other relevant documents (eg, advertisements) must be submitted to an IRB/IEC by the Investigator and reviewed and approved by the IRB/IEC before the study is initiated.
- Any amendments to the protocol will require IRB/IEC approval before implementation of changes made to the study design, except for changes necessary to eliminate an immediate hazard to study participants.
- The Investigator will be responsible for the following:
 - Providing written summaries of the status of the study to the IRB/IEC annually or more frequently in accordance with the requirements, policies, and procedures established by the IRB/IEC. Determining whether an incidental finding should be returned to a participant and, if it meets the appropriate criteria, to ensure the finding is returned (an incidental finding is a previously undiagnosed medical condition that is discovered unintentionally and is unrelated to the aims of the study for which the tests are being performed). The following should be considered when determining the return of an incidental finding:
 - The return of such information to the study participant (and/or his/her designated healthcare professional, if so designated by the participant) is consistent with all applicable national, state, or regional laws and regulations in the country where the study is being conducted, and,
 - The finding reveals a substantial risk of a serious health condition or has reproductive importance, AND has analytical validity, AND has clinical validity,
 - The participant in a clinical study has the right to opt out of being notified by the Investigator of such incidental findings. In the event that the participant has opted out of being notified and the finding has consequences for other individuals, eg, the finding relates to a communicable disease, Investigators should seek independent ethical advice before determining next steps.

- In case the participant has decided to opt out, the Investigator must record in the site medical files that she/he does not want to know about such findings.
- Notifying the IRB/IEC of SAEs or other significant safety findings as required by IRB/IEC procedures,
- Providing oversight of the conduct of the study at the site and adherence to requirements of 21 Code of Federal Regulation (CFR), ICH guidelines, the IRB/IEC, European regulation 536/2014 for clinical studies (if applicable), and all other applicable local regulations.

As applicable, according to Directive 2001/20/EC, the Sponsor will be responsible for obtaining approval from the Competent Authorities of the EU Member States and/or Ethics Committees, as appropriate, for any amendments to the clinical trial that are deemed as "substantial" (ie, changes which are likely to have a significant impact on the safety or physical or mental integrity of the clinical trial participants or on the scientific value of the trial) prior to their implementation.

